#### **4.4.2.1 Reduction in Pain Interference**

The degree to which shoulder pain interferes with daily activities will be assessed using Question 9 of the BPI (BPI9). This question asks the subject to rate the degree to which their pain has interfered with general activity, mood, walking ability, normal work, relations with other people, sleep, and enjoyment of life on a scale of 0 to 10, where 0 is “does not interfere” and 10 is “completely interferes”. The mean of these seven scores will be calculated to obtain the pain interference score. This pain interference endpoint will assist in assessing the impact of pain on activities of daily living and quality life. There is a strong relationship between the severity of post-stroke shoulder pain and BPI9 (Chae et al., 2007). Previous studies that evaluated the impact of neurostimulation therapy on post-stroke shoulder pain showed a significant reduction in the pain interference score when compared to controls (Chae et al., 2005; Yu et al., 2004). Similarly, we anticipate observing an improvement in pain interference in our study.

#### **4.4.2.2 Pain-free passive range of motion (ROM)**

Pain will also be assessed using the pain-free shoulder external rotation ROM assessment. Following stroke, the shoulder often demonstrates a decreased range of motion (Fugl-Meyer, 1980). This decrease in ROM is associated with shoulder pain (Bohannon et al., 1986). In order to measure the pain-free passive ROM, stimulation will be turned off (for at least one hour prior to the study visit) [REDACTED]

Assessing the pain-free passive ROM is common in both clinical research and clinical practice as an objective measurement of pain (Chantraine et al., 1999; Faghri et al., 1994; Chae et al., 2005; Renzenbrink and IJzerman, 2004). Results will be analyzed to determine what impact, if any, the SPR System has on pain-free passive ROM. We expect no worsening of the pain-free ROM and will review the results to determine the usefulness of this measure for our pivotal study on the implantable system.

#### **4.4.2.3 Medical Outcomes Study Short Form (SF-36v2)**

It is important to measure the health-related quality of life (HRQOL) in chronic pain studies, as pain is known to impact daily activities (Dworkin et al., 2005). The SF-36v2 (Ware and Sherbourne, 1992) will be administrated throughout the study to assess the change in HRQOL between the pre- and post-treatment periods. The SF-36v2 is a generic health survey designed to assess basic physical functioning and emotional well-being regardless of the disease or treatment. The 36 items are grouped into eight domains: physical functioning, role limitations due to physical problems, social functioning, bodily pain, general mental health, role limitations due to emotional problems, vitality, and general health perceptions. The SF-36v2 is the most commonly used generic measure of HRQOL and has shown acceptable reliability and validity in stroke populations (Anderson et al., 1996; Dorman et al., 1998). Results of the SF-36v2 will be analyzed to determine the instrument’s ability to detect changes resulting from

SPR therapy [REDACTED]

[REDACTED] In particular, results will be evaluated to ensure that there is no worsening of HRQOL.

#### **4.4.2.4 Patient Global Impression of Change (PGIC) Scale**

Participant ratings of global improvement are one of the core outcome domains in chronic pain studies (Dworkin et al., 2005). The Patient Global Impression of Change (PGIC) scale will be administered to assess subject perception of overall improvement (Guy, 1976). The PGIC scale asks subjects to rate their improvement with treatment on a 7-point scale that ranges from “very much worse” to “very much improved”. The scale provides subjects the opportunity to combine all of the components of their experience into one overall measure and allows clinicians to assess the clinical significance of each subject’s improvement or worsening over the course of the study. We expect the majority of subjects to demonstrate a positive response by selecting one of the three positive answers: 1) minimally improved, 2) much improved, or 3) very much improved.

#### **4.4.2.5 Beck Depression Inventory Second Edition (BDI-II)**

Chronic pain has both sensory and emotional aspects, making it important to measure depression in pain treatment studies (Leavitt et al., 1978; McWilliams et al., 2003). [REDACTED] we will be using the Second Edition of the Beck Depression Inventory (Beck et al., 1961). The BDI-II contains 21 groups of four statements, each group describing a depressive symptom. The respondent is to select the statement that best describes the severity of the given symptom. The BDI-II is recommended by the IMMPACT panel to measure emotional functioning. It has been used extensively in chronic pain clinical trials and has strong evidence of reliability, stability, and validity (Segal et al., 2008; Harris et al., 2008).

[REDACTED]

#### **4.4.2.6 Device Performance and User Satisfaction**

The performance of the SPR Implant System will be evaluated at all follow-up visits.

[REDACTED]

[REDACTED]

A physical examination of the Implantable Lead site and of the IPG pocket site will be performed at each of the follow-up visits. Physical examination of the sites will be used to evaluate the subject for potential adverse events as well as stability of the lead and IPG.

[REDACTED] We  
will monitor subject charging patterns and evaluate ease of use.

Sponsor-developed satisfaction surveys will be administered to both the subjects and the clinicians to determine the overall satisfaction with the therapy and the technology. The results of the surveys will validate the study design and technology. The SPR System Subject Satisfaction Surveys will be administered to determine the overall subject satisfaction with the therapy and the usability of the SPR System. The SPR Trial Stage Subject Satisfaction Survey will be administered at the conclusion of the Trial Stage and the SPR Implant Stage Subject Satisfaction Survey will be administered at the 12-week and 12-month IPG Stim ON follow-up visits. In addition, two sponsor-developed Clinician Satisfaction Surveys will be administered. One survey will be administered to the Principal Investigator (the Physiatrist) and includes questions pertaining to both the SPR Trial and Implant Stages. The second survey will be given to the Investigator implanting the device (the surgeon) and includes questions related to the SPR Implant Stage procedure and the SPR therapy.

[REDACTED]  
These sponsor-generated surveys are being piloted during this study.

#### **4.4.2.7 Economic Impact of Shoulder Pain**

At baseline, subjects will be asked to document pain medication, doctor visits, supplies (such as slings), related treatments (such as physical therapy for pain or psychotherapy for depression), need for caregivers, time spent in skilled nursing facilities, and lost work due to their shoulder pain. Subjects will be asked to recall this data for the 6-months prior to study enrollment. This raw data will be gathered from the subject. The Sponsor will then assign national average costs to each treatment used to determine the overall economic impact of shoulder pain.

Subjects will be permitted to complete this survey at home. The survey will not be monitored during routine monitoring visits and missing data will be not queried as is it anticipated that subjects may not be able to provide all the information requested.

#### 4.4.2.8 Quantitative Sensory Testing (QST)

Quantitative Sensory Testing (QST) may be performed in order to determine if specific demographic, clinical, anatomic, physiologic, and psychological factors will categorize subgroups of participants according to their response to percutaneous IM PNS. The objective of the QST testing is to determine when a subject can first feel a sensation and when the sensation becomes painful.

The QST testing is optional and all elements of the QST may not be completed if the testing is found to take an excessive amount of time or if the subject is, for any reason, unable or unwilling to complete all of the testing. Subjects will be informed that there is a potential for skin irritation immediately following this testing.

QST testing will be performed at Visits 1,4,5, pre-6, 9, 11, and 13 and will consist of the following elements:

All measures described below, with the exception of the Conditioned Pain Modulation (CPM) protocol described below, will be obtained at three skin test sites: [REDACTED]

[REDACTED] The stimulation sites for the CPM are described in the section for “measures of central pain modulation,” below.

[figure not shown]
**General QST testing information:** Testing will be conducted in a quiet setting and subjects will be seated in a comfortable reclining chair. Subjects will be given a brief introductory session of the QST procedures. The introductory session will allow the subject to experience the range of stimuli to be presented and to familiarize themselves with the instructions for each test procedure.

Subjects will be instructed that they can stop the procedures at any time for any reason without penalty. All stimuli (with the exception of the cold water bath) will be presented with hand-held devices that can quickly be removed from the test site by the experimenter, or from which the subject can withdraw from the stimulus without constraint. All procedures to be used in this study, have been used in numerous published studies in a variety of subject groups and, for most

tests, involve threshold-level pain sensations induced by brief presentations of noxious stimuli.

Test administration will occur in the order that the tests are described below and will take approximately 2.5 hours to complete. Each type of test will be conducted at all 3 skin test sites before moving to the next test procedure, so that stimulation at one body site will occur for a brief period of time followed by at least 3 minutes of "rest" before stimulation occurs at that site again. Longer breaks of stimulation will be utilized between the series of temporal summation trials and between the temporal summation protocol and CPM protocol, to insure that any pain from the procedure has resolved.

**QST Instruments and Equipment:**

**Measures of Tactile/Mechanical Sensory Function:**

[REDACTED] *Tactile/touch detection thresholds* will be measured using four series of stimulus presentations of the graded TouchTest monofilaments (North Coast Medical) at each test site.

[REDACTED]

- *Vibration detection thresholds* will be measured using the VSA component of the TSA-II device (Medoc, Ltd.).

[REDACTED] Three trials will be performed at each test site.

**Measures of mechanical pain sensory function:**

[REDACTED] *Pin prick pain threshold* will be measured using graded force mechanical probes with small probe tips (MRC Systems).

[REDACTED]

[REDACTED] *Pressure pain threshold* will be measured using a manual pressure algometer.

[REDACTED]

**Measures of thermal detection and thermal pain function:** The TSA-II (Medoc, Ltc.) will be used to deliver thermal stimuli via a thermal probe [REDACTED]

[REDACTED] The probe will be held lightly against the skin as the temperature increases (for warm detection and hot pain thresholds) or decreases (for cool detection and cold pain thresholds) from a baseline temperature that approximately matches the neutral skin surface temperature (32°C). Subjects will be instructed to verbally respond when the desired sensation is reached.

[REDACTED]

Each type of sensation threshold (cool detection, warm detection, cold pain, hot pain) will be measured three times at each test site.

**Measures of temporal summation of pain:** Repeated administration of brief noxious stimuli will be performed to investigate temporal summation of pain (increased sensation of pain with repetitive stimulation at the same stimulus intensity). Two types of stimuli will be used for this: mechanical stimuli (using the pin prick stimulators) and thermal stimuli (using the TSA-II device).

**Measure of conditioned pain modulation:** The conditioned pain modulation (CPM) protocol consists of two types of stimuli: the test stimulus (which will be a brief thermal stimulus set at a mild to moderately painful temperature, [REDACTED] and the conditioning stimulus (a cold water bath set at a temperature [REDACTED]). The test stimulus will be presented to the volar forearm at the beginning of the CPM protocol and the subject will be asked to rate the pain intensity of the sensation produced by this stimulus. The subject will then submerge his/her foot into the cold water bath [REDACTED]. The same thermal stimulus will then be presented to [REDACTED] forearm again and the subject will be asked to rate the pain intensity of the stimulus. One trial of CPM will be performed.

#### **4.4.2.9 Reduction in arm impairment and improvement in Activities of Daily Living using the Stroke Upper Limb Capacity Scale (SULCS)**

The Stroke Upper Limb Capacity Scale (SULCS) will be used to test the hypothesis that a reduction in post-stroke shoulder pain will be associated with reduction in arm impairment and improvement in activities of daily living (ADLs) compared to baseline. [Roorda, 1992] The SULCS will be performed at Visits 1,4,5, pre-6, 9, 11 and 13.

The SULCS is a validated upper limb capacity scale which includes tasks directly related to activities of daily living individuals experience in their home environment. The SULCS consists of 10 items, with each item having a possible score of 0 or 1: 3 items for arm capacity without active hand capacity; 4 items for

arm capacity and basic hand capacity; and, 3 items for complex hand capacity. The SULCS takes approximately 10-15 minutes to complete.

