#### 5.4.3 Secondary Endpoint Analysis

As with the primary endpoint, we will analyze what effect, if any, the treatment has on pain interference (BPI9), Pain Free Passive Range of Motion, SF-36v2, BDI-II, the Patient Global Impression of Change scale, the SULCS, and subject satisfaction. QST testing is optional and thus an analysis will be completed if sufficient data are gathered.

Pain interference (BPI9), Pain Free Passive Range of Motion, SF-36v2, and BDI-II, the SULCS, and QST Testing are collected at the End of Trial Stage, 3-weeks, 12-weeks, 6-months, 9-months, and 12-months post IPG Stim ON. These secondary endpoints will be compared to the End of Sham. In addition, the pain interference (BPI9) is also collected at 6-weeks, 24-months and 36-months post IPG Stim ON and will be compared to End of Sham. As with the primary endpoints, subjects demonstrating a negative placebo effect for secondary endpoints will be compared to Baseline.

Results of the Patient Global Impression of Change scale and the subject satisfaction survey will be independently summarized to assess for a positive response indicating overall subject satisfaction with the system and therapy.

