#### **6.1.2.4 Overall study success**

Overall study success is defined by the success rate across all subjects participating in each stage, and is expected to exceed the historically observed success rate █ based upon previous and ongoing studies that demonstrated a █ success rate among subjects treated with stimulation therapy (Yu et al., 2001a; Chae et al, 2005; Chae et al., 2013; Wilson et al., 2014; as well as the present study and an unpublished randomized controlled trial).

A test of significance will be carried out to test the null hypothesis that the success rate █ or less versus the alternative that the true success rate exceeds █. In addition, a 95% confidence interval for the true success rate will be reported with the expectation that the lower limit of the interval will exceed █

All treatment failures, including any subjects who had an Implant Stage system removed due to an adverse event, will also be analyzed as part of this analysis.

Finally, a logistic regression will be reported, treating subject success as the binary outcome and baseline BPI as a possible explanatory variable. Other subject characteristics, such as time post-stroke, cortical vs. subcortical, right vs. left affected shoulder, and subluxation versus non-subluxation will be examined via a covariate analysis.

Secondary endpoints will be assessed using non-parametric tests. The Wilcoxon signed-rank test will be used to examine the difference of each endpoint for each subject. We will also investigate the mean improvement by reporting the results using a one-sample t-test.

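### SULCS is meant to test whether pain reduction goes with better arm function, but the planned tests look only at SULCS's own change and cannot address that association

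*Combined protocol and SAP*

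**What the plan says.** Section 4.4.2.9 gives SULCS its purpose: it "will be used to test the hypothesis that a reduction in post-stroke shoulder pain will be associated with reduction in arm impairment" and with better activities of daily living, compared to baseline. The scale has ten items scored 0 or 1, so the total runs from 0 to 10. On timing: "The SULCS will be performed at Visits 1,4,5, pre-6, 9, 11 and 13".

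The synopsis describes the same endpoint differently, as the impact of therapy on arm impairment.

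Section 5.4.3 follows the synopsis. It sets out to analyse what effect the treatment has on each secondary endpoint, SULCS included. On the reference visit it says "These secondary endpoints will be compared to the End of Sham", with Baseline used instead for subjects who show a negative placebo effect.

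Section 6.1.2.4 supplies the tests: "The Wilcoxon signed-rank test will be used to examine the difference of each endpoint for each subject" and "We will also investigate the mean improvement by reporting the results using a one-sample t-test". Its one regression models subject success on baseline BPI, with subject characteristics as further covariates.

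Section 6.2 repeats the 12-week analysis at 36 months, noting that most secondary endpoints are not collected then. It adds no association analysis.

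**The concern.** The hypothesis in Section 4.4.2.9 concerns a relation between pain change and SULCS change. The planned tests ask whether SULCS change differs from zero on average. Nothing in Sections 5.4.3, 6.1.2.4 or 6.2 pairs the two changes, and no redaction falls in Section 5.4.3 or in the secondary-endpoint sentences of Section 6.1.2.4 that could hide such an analysis.

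In an uncontrolled series, SULCS could improve for reasons unrelated to pain. Section 2.2.3 says stimulation can activate paralysed muscle and cites a surface-stimulation trial in which recovery of arm motion improved. Up to seven administrations of the scale also leave room for practice and time effects.

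Section 4.4.2 says the secondary instruments are being assessed for use in the pivotal study. If a mean SULCS gain were read as evidence that pain relief goes with function, that reading would enter the pivotal design without having been tested.

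**Working it through.** The plan gives no SULCS figure to reproduce, so the check is mainly a comparison of texts. The arithmetic below only illustrates it.

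**1. What each test addresses.** Let D be a subject's SULCS change and R the same subject's BPI3 reduction.
- Hypothesis in Section 4.4.2.9: the correlation of D and R is above zero.
- Signed-rank and one-sample t-test in Section 6.1.2.4: D is centred on zero. R does not enter.
- Logistic model in Section 6.1.2.4: success given baseline BPI and subject characteristics. D does not enter, and every example listed is a baseline feature.

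The mean of D and its correlation with R can vary separately, so a result on one does not settle the other.

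**2. No association, but a mean SULCS gain.** Simulated trials with D and R independent, two-sided 0.05. The means and SDs of D are assumptions. Share of trials in which the signed-rank test is significant:

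| Assumed mean, SD of D | n=20 | n=30 | n=45 |
|---|---|---|---|
| 0.6, 1.2 | 54% | 71% | 89% |
| 0.3, 1.2 | 17% | 24% | 36% |
| 0.6, 2.0 | 25% | 34% | 48% |
| 0.3, 2.0 | 9% | 11% | 17% |

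A Spearman test of D against R stays near 5% throughout. The table shows the ordinary power of the signed-rank test for a real SULCS gain; these are correct rejections of that test's own null. The spread from 9% to 89% shows that no single figure can be attached to the problem.

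**3. Association, but no mean gain.** With an assumed correlation of 0.5 and mean D of zero, the signed-rank test is significant in about 5% of trials at n=45 and n=18. Spearman is significant in 91% and 51%.

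**4. Are the data there?** BPI3 and SULCS are both taken at Visits 1, 4, 5, 9, 11 and 13. They are not paired at Visit Pre-6, where the pain score comes from a follow-up call, or at Visit 10, where Section 4.4.2.9 schedules no SULCS. (Section 5.4.3 lists SULCS among measures taken at 3 weeks, 12 weeks and 9 months, which Section 4.4.2.9 does not schedule; the two lists should be aligned.)

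**5. Precision.** By the Fisher z approximation, the half-width of the 95% CI on the z scale is 1.96/√(n−3), and the smallest correlation detectable with 80% power is tanh[(1.960+0.842)/√(n−3)].
- n=45: 1.96/√42 = 0.302; tanh(0.432) = 0.41
- n=30: 1.96/√27 = 0.377; tanh(0.539) = 0.49
- n=18: 1.96/√15 = 0.506; tanh(0.723) = 0.62

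For an observed 0.5 (z = 0.549) at n=30, the interval is tanh(0.549 ± 0.377), or 0.17 to 0.73. The number with SULCS data is not stated. Section 4.5.1 limits it to subjects enrolled after the scale was added, so 45 is a ceiling. These are approximations for continuous data; the coarse 0–10 score will do somewhat worse.

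**The case against.** The strongest counter-argument is that Section 4.4.2.9 need not be read as a subject-level correlation. The reference to baseline also fits a looser meaning: a treatment that reduces pain is accompanied by better arm function. On that reading the plan tests what the synopsis describes, and one loosely worded sentence is the only problem. This stands far enough that rewording the sentence is a full remedy. It does not remove the mismatch, because the sentence names pain reduction, not treatment, as the thing associated with function.

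Three stronger readings are tempting, and the documents do not support them.
- *The trial would declare the hypothesis supported on a SULCS gain.* No decision rule, significance level or claim is set for SULCS. That is a risk of interpretation, not a planned conclusion.
- *The simulated percentages are a false-positive rate.* They are power at assumed values, and they move widely with those values.
- *QST has the same gap.* Section 4.4.2.8 does give its purpose as finding factors that "will categorize subgroups of participants according to their response to percutaneous IM PNS". But QST is optional, Section 5.4.3 makes its analysis conditional on enough data, the synopsis endpoint is change in thresholds, and the covariate list in Section 6.1.2.4 is only illustrative. Baseline QST could enter the existing success model as a subject characteristic.

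A correlation also does not exclude rival explanations: time or direct muscle stimulation could move pain and SULCS together. It would show association only, but association is what Section 4.4.2.9 names.

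**Conclusion.** The mismatch is real and follows from the text alone. Carried out as written, the plan answers whether SULCS changed after treatment and leaves the association hypothesis unanswered, whatever the SULCS result. This conclusion needs no numerical assumption. The percentages above do, and they illustrate direction only.

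The importance is minor. SULCS is one secondary endpoint in a pilot, was added after enrolment began, and bears on no primary endpoint, safety or sample-size decision. The paired data will exist in any case. What would be lost is prespecification. The choice of interval should not be made after the results are seen, and the documents already point two ways: baseline in Section 4.4.2.9, End of Sham in Section 5.4.3.

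**What to change.** Add to Section 5.4.3 wording such as: *The SULCS hypothesis is assessed by the Spearman correlation, with 95% CI, between SULCS change (later minus earlier) and BPI3 reduction (earlier minus later) over the same interval, so that a positive value supports it. The main interval is Visit 1 to Visit 5; Visit 4 to Visit 5 is supportive. Fixed intervals replace the negative-placebo reference rule for this analysis. SULCS change is also shown for Trial Stage successes and failures.*

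Visit 1 to Visit 5 is the main interval because Section 4.4.2.9 names baseline. Fixed intervals are needed because the negative-placebo rule could otherwise give the two measures different reference visits in the same subject.

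Keep the one-sample SULCS tests as the analysis of treatment impact, and state that they are not read as support for the association. In the Implant Stage (about 18 subjects) report any correlation descriptively.

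Alternatively, reword Section 4.4.2.9 as a hypothesis about SULCS change after treatment, in line with the synopsis, and leave the analysis as it is.

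The cost is a few sentences and one table from data already collected. The estimate will be imprecise, since only subjects enrolled after SULCS was added contribute, and it cannot establish causation. Baseline QST may be named as an optional exploratory covariate in the success model; nothing more is needed there.
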